2.6.1 Screening

Screening: Following informed consent, patients will undergo screening assessments to determine that all inclusion/exclusion criteria are met prior to randomization or receiving the study drug treatments.

The following screening information will be collected and entered into the study case report forms (CRFs) and/or web-based data collection system.

1. Physician names and contact information, general medical and surgical histories, including suicidality, co-morbidities, concurrent medications, and allergies.

a. Excluded Concomitant medications

- Anti-B-cell therapy:
 - Wash out of 5 therapeutic half lives after prior B-cell therapy, or until pharmacodynamic effect would be minimal (e.g., 1 year following rituximab)

- 365 days Prior to Belimumab:
 - Any biologic investigational agent (e.g., abetimus sodium, anti CD40L antibody, BG9588/ IDEC 131)
 - Investigational agent applies to any drug not approved for sale in the country in which it is being used
- 180 Days Prior to Belimumab:
 - o Intravenous cyclophosphamide
 - If concomitant use, enhanced safety monitoring required.
 - Serum IgG levels should be measured monthly in this situation
 - Benlysta should be discontinued in subjects with serum IgG levels <250 mg/dL associated with a severe or serious infection
- 30 Days Prior to Belimumab (or 5 half-lives, whichever is greater)
 - Any non-biologic investigational agent
 - Investigational agent applies to any drug not approved for sale in the country in which it is being use
- Live vaccines within 30 days prior to baseline or concurrently with belimumab
- 2. Recording of vital signs and medication regimen.
- 3. Review of medications
- 4. Brief assessment of symptoms.
- 5. Recording of laboratory and clinical testing results.
- 6. Pulmonary function test results (pre/post bronchodilator (BD) spirometry and DLCO).
- 7. Serum cotinine
- 8. Chest CT, with measurement of F_{950}^{35} within the preceding 2 years if available

The screening assessment may take place over more than one day. Eligible patients will then undergo the following tests and procedures prior to randomization:

- Detailed medical history and demographics
- Physical exam to include vital signs and blood pressure.
- Laboratory evaluations specific for Inclusion/Exclusion Criteria to include: CBC, BMP, Liver function tests, HIV, hepatitis B and C tests, IgA, ANA, RF, anti-SSA, anti-Jo-1, anti-CCP, cotinine, urine pregnancy test (if applicable),, IgA, IgG.

Patients who fulfil all entry/exclusion criteria, and agree to participate, will have remaining baseline assessments (spirometry, DLCO, 6MWD, and carotid ultrasounds), blood obtained for experimental immunology assays (see Primary and Secondary Endpoints, Section 2.8) and be randomized to receive one of the study treatments described above in Section 2.3. No more than 30 days should elapse between completion of the eligibility assessments and the first experimental treatment.

Subsequent events include:

2.6.2 Experimental procedures

Day 1 (Initiation of therapy):

Patients will report to a UAB infusion center for the following:

Day 1:

- Directed physical exam that includes vital signs and blood pressure, interval medication and symptom changes.
- Laboratory evaluations (Table 2) to include CBC, BMP (electrolytes, glucose, BUN, serum creatinine), liver function tests (INR, total bilirubin, ALT, AST), pregnancy test, if applicable, (must be < 7 days prior to first dose).
- Adverse Event (AE) assessment.
- First infusion of study drug.

Day 2:

• Phone assessment by study personnel, including an AE assessment

Day 14:

- Directed physical exam that includes vital signs and blood pressure, interval medication and symptom changes.
- Laboratory evaluations (Table 2) to include CBC, BMP (electrolytes, glucose, BUN, serum creatinine), liver function tests (INR, total bilirubin, ALT, AST), pregnancy test, if applicable.
- Second infusion of study drug
- AE assessment

Day 15:

• Phone assessment by study personnel, including an AE assessment

Day 30 (Month 1):

- Directed physical exam that includes vital signs and blood pressure, interval medication and symptom changes.
- Laboratory evaluations (Table 2) to include CBC, BMP (electrolytes, glucose, BUN, serum creatinine), liver function tests (INR, total bilirubin, ALT, AST), and IgG, pregnancy test, if applicable.
- Spirometry (post-BD)
- Third infusion of study drug
- AE assessment

Day 31:

• Phone assessment by study personnel, including an AE assessment

Day 60 (Month 2):

- Directed physical exam that includes vital signs and blood pressure, interval medication and symptom changes.
- Laboratory evaluations (Table 2) to include CBC, BMP (electrolytes, glucose, BUN, serum creatinine), liver function tests (INR, total bilirubin, ALT, AST), pregnancy test, if applicable, and IgG.
- Fourth infusion of study drug

• AE assessment

Day 61:

• Phone assessment by study personnel, including an AE assessment

Day 90 (Month 3):

- Directed physical exam that includes vital signs and blood pressure, interval medication and symptom changes.
- Laboratory evaluations (Table 2) to include CBC, BMP (electrolytes, glucose, BUN, serum creatinine), liver function tests (INR, total bilirubin, ALT, AST), pregnancy test, if applicable, and IgG.
- Spirometry (post-BD)
- Fifth infusion of study drug
- AE assessment

Day 91:

• Phone assessment by study personnel, including an AE assessment

Day 120 (Month 4):

- Directed physical exam that includes vital signs and blood pressure, interval medication and symptom changes.
- Laboratory evaluations (Table 2) to include CBC, BMP (electrolytes, glucose, BUN, serum creatinine), liver function tests (INR, total bilirubin, ALT, AST), pregnancy test, if applicable, and IgG.
- Sixth infusion of study drug
- AE assessment

Day 121:

• Phone assessment by study personnel, including an AE assessment

Day 150 (Month 5):

- Directed physical exam that includes vital signs and blood pressure, interval medication and symptom changes.
- Laboratory evaluations (Table 2) to include CBC, BMP (electrolytes, glucose, BUN, serum creatinine), liver function tests (INR, total bilirubin, ALT, AST), pregnancy test, if applicable, and IgG.
- Spirometry (post-BD)
- Seventh infusion of study drug
- AE assessment

Day 151:

• Phone assessment by study personnel, including an AE assessment

Day 180 (Month 6):

- Directed physical exam that includes vital signs and blood pressure, interval medication and symptom changes.
- Laboratory evaluations (Table 2) to include CBC, BMP (electrolytes, glucose, BUN, serum creatinine), liver function tests (INR, total bilirubin, ALT, AST), pregnancy test, if applicable, and IgG.

- Eight and final infusion of study drug
- AE assessment

Day 181:

• Phone assessment by study personnel, including an AE assessment

Day 210 (Month 7):

- Directed physical exam that includes vital signs and blood pressure, interval medication and symptom changes.
- Laboratory evaluations (Table 2) to include CBC, BMP (electrolytes, glucose, BUN, serum creatinine), liver function tests (INR, total bilirubin, ALT, AST), cotinine, pregnancy test, if applicable, and IgG.
- Spirometry (pre/post-BD)
- 6MWD
- Carotid ultrasound
- AE assessment

Day 240 (Month 8):

• Phone assessment by study personnel, including an AE assessment. A variance of 5 days will be allowed for these telephone contacts to account for weekends or holidays.

Day 300 (Month 10):

• Clinic visit and pregnancy test, if applicable (females with childbearing potential). Other subjects will have phone assessment by study personnel, including an AE assessment.

2.6.3 Other Variances

A variance of +/-5 days will be allowed for clinic visits and treatments, to account for weekends, holidays or other logistic problems. A variance of 10 days will be allowed for the surveillance visits on day 210, and day 300 (if applicable), for the same reasons.

2.6.4 Specimen Collection and Management

Specimen Collection / Documentation: An extra 29 ml of blood for experimental immunologic research studies and endpoint measures will be obtained pretreatment, and on days 30, 90, 150, and 210 after the start of therapy (Table 2). The peripheral blood will be processed to separate mononuclear cells, plasma, and sera, which will be aliquoted, and frozen (-80°) until used in batched assays. These assays will be carried out in the laboratories of [name].

Each research sample will be labeled with subject's unique identifier, sample date, and sample collection time. The code number and date on which the specimen is frozen, all other information about the specimen, and subsequent processing will be entered on a specimen processing worksheet.

Covariate information, e.g., concomitant medications, laboratory values, etc., will be obtained at each time point.

Specimen Handling and Labeling (De-Identification)

All research specimens and all records associated with the samples will be labeled only with a unique code that links to the trial data but contains no personal identifiers. The information linking these code numbers to the corresponding subject's identity will be kept in a secure location in the contact Pl's office, and will not be available to staff managing samples at the research laboratory.

Specimen Management and Storage: Specimens in excess of immediate assay requirements may be stored indefinitely in a secured freezer under the control of the responsible PI. The coding information linking patient identifiers to the stored samples will be maintained in a locked, secure area that will be accessible only to the study investigator. Subjects may request to have their samples destroyed at any time. These samples will be destroyed immediately upon receipt of the subjects' written request to do so.

Restrictions to Direct Access of Specimens: Specimens will be kept in the responsible study investigators' laboratory indefinitely and will be under the control of the PIs. Investigators or other personnel not involved with the management or operations of the study are not permitted direct access to the specimens.

2.7 STUDY ENDPOINTS

2.7.1. The Primary End-Point:

The primary endpoint of this trial is a reduction of circulating levels of anti-GRP78 Peptide 25, a clinically relevant surrogate biomarker of "autoimmunity" in these patients. Plasma concentrations of the anti-GRP78 autoantibodies will be measured pre-treatment, and at 1, 3, 5, and 7 months after treatment start.

General: Heparinized blood for end-point measures will be obtained from subjects by venous phlebotomy. Gentle centrifugation will separate cells from plasma, which will then be aliquoted and appropriately stored for assays of anti-GRP78 IgG (primary endpoint) and anti-pneumococcal antibodies (a secondary endpoint). A separate unanticoagulated tube (red top) will be used to procure sera. Peripheral blood mononuclear cells (PBMNC) will be isolated from the residual heparinized specimen by resuspension and density gradient centrifugation. PBMNC will be used for B-cell studies (a secondary endpoint), and residual cells will also be stored frozen as dry pellets and in RNase protection media for potential later use (e.g, cloning and sequencing autoreactive B-cell IgG).

Anti-GRP78 IgG levels will be measured in serial specimens by a custom ELISA that has already been developed, validated, and employed (see Figs. 4,5). In brief, biotinylated GRP78 Peptide 25, which was synthesized by Thermo Scientific (Waltham, MA) is diluted to 0.5ug/ml in PBS and added to streptavidin-coated ELISA plate wells and incubated overnight at 4°C. After thorough washing and blocking, patient plasma specimens (see Section 2.8.2) are added to the wells at 1:100 dilutions and incubated for 2 hours at room temperature. Following additional washes, alkaline phosphatase-conjugated goat anti-human antibody (1:5000 dilution) is added, incubated, and color developed with a pNPP substrate system (KPL, Gaithers-burg, MD). Optical densities (OD) are determined at 405 nm.

ELISAs against GRP78 and epitopes within this molecule are accurate and reproducible. We used identical aliquots of several specimens in assays performed by multiple different lab operators, separated temporally by up to 1 year. Despite these variables, the ELISA yielded concordant values with $r \ge 0.96$. Similarly, serial anti-GRP78 IgG measures in specimens collected after two-year intervals from a group of COPD patients yielded r > 0.82. Most of the differences in OD values in the serial

measures seemed to be inversely concordant with interval changes of patient's clinical status (e.g., anti-GRP78 OD tended to increase as their lung disease severity got worse).

2.7.2. Secondary End-Points

Specific Aim 2 Endpoints: The secondary endpoints of this trial are: 1.) treatment effects on concentrations of pneumococcal polysaccharide-binding antibodies by ELISA^{33,36} 2.) treatment effects on absolute numbers and phenotypes of circulating B-cells by flow cytometry,⁸ and 3.) Adverse event comparisons.

Secondary endpoint #1. (anti-pneumococcal antibodies) and #2. (B-cells) will be assessed among blood specimens obtained prior to treatment, and at 1, 3, 5, and 7 months after treatment starts. Secondary endpoint #3 (AE) will be assessed at each clinic visit, telephone encounter and in communications initiated by subjects or study personnel at any other interval.

a.) Pneumococcal polysaccharide-binding antibody concentrations in plasma will be measured pre-treatment, and compared to results at the aforementioned intervals after treatment started. The ELISA methodology is straightforward, highly standardized, and fully detailed previously.³⁶

b.) B-cell numbers and phenotypes will be assessed at the same time-points. Method-ologies are also well established and have been previously detailed.⁸ In brief, B-cells will be stained with panels of fluorochrome-conjugated monoclonal antibodies and characterized by flow cytometry. B-lymphocytes will be identified as CD3⁻/CD14⁻/CD16⁻/CD19⁺ cells, and further stratified for comparisons as transitional (IgD⁺/CD38⁺⁺), IgM⁺ IgA⁻ IgG⁻ switched memory (IgD⁺/CD27⁺), IgG⁺ switched memory (IgD⁻/CD27^{+/-}), and plasmablasts (CD19^{lo/+}, CD20⁻, CD38⁺⁺, IgD⁻, CD27⁺⁺).⁸

c.) Adverse Events: The NCI Common Toxicity Criteria Scale will be used to define grades (severity) of adverse events and toxicities. An adverse event is defined as any untoward medical occurrence in a subject, regardless of its relationship to these treatments. Toxicity is an adverse event with a direct relationship to the study drug. All toxicities are adverse events, but not all adverse events are toxicities. Case report forms (CRF) will require responses to all adverse events (and negatives), with a particular focus on allergic reactions, infections (including location and organism), and neuropsychiatric symptoms. Recording adverse events in pre-specified checklists (and free text entries) in all subjects will guard against unintended bias.

2.7.3 Other Measures that are not a Formal End-Point: Carotid artery ultrasounds (US) will be obtained in participants at baseline evaluations and at the conclusion of formal observations (day 210), in order to determine carotid intimal medial thicknesses (IMT). We do not believe there is a high likelihood there will be a significant treatment effect, given the small number of participants and short duration of therapy in this exploratory trial. Nonetheless, these tests will establish the feasibility of using these assays in subsequent larger and longer trials to examine effects of autoantibody reduction in COPD patients.

2.8 DATA AND POWER ANALYSES

2.8.1 Primary Endpoint Data Analyses:

Baseline demographic and clinical data of participants will be summarized using means (with standard deviations) and medians (with inter-quartile ranges) for continuous variables, and counts and percentages for discrete variables, stratified by treatment group. Differences among groups (to examine the randomization effectiveness), will be assessed by t-tests, or by Fisher's exact test for discrete data, recognizing the limited power of our small trial.

Repeated measures linear mixed models will be used to evaluate differences of immunological parameters (continuous variables) that comprise the primary, and most second endpoints. These models will track the changes over time as well as allow for missing observations, which should be minimal. In general, analyses will follow intention to treat principles, with the last observed outcome over all time points being used as the primary measure for a given variable.

The sample size of 18 subjects for this clinical trial is based on exposing a minimum number of patients to potential risks of the experimental therapy, while having the potential to obtain useful information. Given that this trial is unprecedented, it is impossible to use preliminary data to definitively derive power analyses. Indeed, an important purpose of this study is to generate credible and relevant preliminary data in this population to power subsequent larger trials. Trials to detect clinical efficacy (e.g., change in pulmonary function tests, reductions in acute exacerbations, etc.) will almost certainly require treatment of many subjects over prolonged periods.

With these limitations in mind, we can assume belimumab effects in COPD patients are similar to those among patients with SLE. Thus, we can expect to see reductions of anti-GRP78 autoantibody concentrations by ~30%, in addition to ~50% reductions of several circulating B-cell subpopulations, by or after approximately 6 months of therapy. With respect to the primary endpoint (reduction of anti-GRP78 IgG): If the true difference in the experimental and control means is 30%, with standard deviations that are two–thirds of this (20%), we will need to study 12 experimental subjects and 6 control subjects to reject the null hypothesis that the population means of the experimental and control groups are equal, with probability (power) 0.8. The Type I error probability associated with this test of the null hypothesis is 0.05.

The 2:1 experimental arm: control enrollment will increase the amount of data regarding effects and safety of this drug in COPD patients, and only increases the necessary subject number to reach 80% power by two, compared to 1:1 enrollment.

2.8.2 Secondary Endpoint Data Analyses: Analyses will again follow intention to treat principles, with the last observed outcome over all time points being used as the primary measure for a given variable. Multiple imputation will be used based on subject characteristics to assess the obvious issues with last observations carried forward in these analyses. Trajectories over time, for a given patient and outcome measure, will be displayed via line graphs, and assessments conducted using linear mixed models on the repeated time points. Comparisons between the treatment arms of the polysaccharide binding assay concentrations and B-cell parameters at various time points will be made using repeated measures techniques. Transformations of these tests may be needed, such as velocities, if many individuals are unable to complete the entire treatment protocol. The proportion of subjects with adverse events and the count of adverse events per subject will be compared by treatment using Fisher's exact test and the exact Poisson tests, respectively.

2.8.3 Interim Analysis: Since the primary endpoint of this trial is a laboratory test and surrogate biomarker, rather than a clinical outcome parameter, and the subject number is small, no interim analysis will be conducted for efficacy.

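### Section 2.8.1 does not say how the pre-treatment anti-GRP78 value enters the primary comparison; naming one model with baseline as a covariate settles this at almost no cost

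*Combined protocol and SAP*

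**What the plan says.** Section 2.7.1 defines the endpoint: "The primary endpoint of this trial is a reduction of circulating levels of anti-GRP78 Peptide 25". It schedules samples before treatment and at 1, 3, 5 and 7 months, but gives no formula for the reduction.

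Section 2.8.1 says "Repeated measures linear mixed models will be used to evaluate differences of immunological parameters", and adds: "These models will track the changes over time as well as allow for missing observations". It then says that analyses will in general follow intention to treat, "with the last observed outcome over all time points being used as the primary measure for a given variable". The power paragraph in the same section describes a two-group test, "to reject the null hypothesis that the population means of the experimental and control groups are equal", and does not say whether the 20% SD is that of a level or of a change.

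No section names a baseline term, a covariate or a primary contrast for this endpoint. Section 2.7.2 says that pneumococcal antibody will be compared with its pre-treatment value; section 2.8.1 has no matching sentence for anti-GRP78. Section 2.8.2 repeats the last-observed rule for the secondary endpoints.

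**The concern.** The text fits at least three analyses: unadjusted last values, change from baseline, or follow-up values with baseline as a covariate. A mixed model can be set up in any of these ways.

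Two things are at stake. First, anti-GRP78 appears to be a stable characteristic of a patient. An analysis that ignores the pre-treatment value leaves the between-patient spread in the error term, although that value is already collected in every subject. Second, with 12 against 6 the arms can easily differ at baseline by chance, and the candidate analyses then give different answers. If the choice is not fixed beforehand, it could be made after the answers are known.

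**Working it through.** **Inputs.** From section 2.8.1: 12 and 6 subjects, difference 30, SD 20, type I error 0.05. The number of sides is not stated; two-sided is assumed because it reproduces the stated power. The difference is treated as additive because no analysis scale is named.

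The correlation r between pre-treatment and follow-up values is an assumption. Section 2.7.1 reports that "specimens collected after two-year intervals from a group of COPD patients yielded r > 0.82", a lower bound, and nothing says that those patients were on belimumab. It also reports r of at least 0.96 for repeat assays of identical aliquots, which serves only as a ceiling. Inclusion criterion 4 admits the upper three quartiles. Cutting a normal distribution at its 25th percentile leaves 53.5% of its variance, so 0.82 becomes 0.82√0.535 / √(0.535 × 0.82² + 1 − 0.82²) = 0.72.

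**The plan's own figure.** SE = 20 × √(1/12 + 1/6) = 20 × 0.5 = 10. Noncentrality = 30/10 = 3.0 on 16 df. Power = 0.804, so the stated 0.8 is reproduced.

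**Formulas.** With level SD σ, equal at both times:
- Unadjusted last value: SD σ, 16 df.
- Change: SD σ√(2(1 − r)), 16 df.
- Covariate: SD σ√(1 − r²), 15 df, with the variance multiplied by 1 + 1/14 for chance imbalance.

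**If 20 is the SD of change**, then σ = 20/√(2(1 − r)):

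| r | σ | Last value | Change | Covariate |
|---|---|---|---|---|
| 0.72 | 26.7 | 0.56 | 0.80 | 0.83 |
| 0.82 | 33.3 | 0.39 | 0.80 | 0.81 |
| 0.90 | 44.7 | 0.24 | 0.80 | 0.79 |

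For example, at r 0.82 the unadjusted SE is 33.3 × 0.5 = 16.7 and the noncentrality is 30/16.7 = 1.80. The covariate SD is 33.3 × √(1 − 0.82²) = 19.1, its SE is 19.1 × 0.5 × √(15/14) = 9.9, and the noncentrality is 3.04. Covariate and change are level near r 0.85. At r 0.96 the covariate has 0.78.

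**If 20 is the SD of level:** unadjusted 0.804; change 0.964 (r 0.72) and 0.997 (r 0.82); covariate 0.974 and 0.997. If r were 0 the covariate would have 0.773.

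**Truncation at entry.** Simulated with the unequal variances that truncation produces, and change SD 20, the covariate has 0.794, 0.786 and 0.778 at restricted r of 0.72, 0.83 and 0.93, against 0.80 for change.

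**Four-visit mixed model.** Simulated month-7 contrast, change SD 20, complete data, equal correlation among all five values, r 0.72/0.82/0.90/0.96:
- No baseline term: 0.58/0.41/0.25/0.13.
- Baseline as a fifth outcome with free means: 0.84 throughout.
- Baseline covariate: 0.87/0.85/0.83/0.82.

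**Chance imbalance.** The baseline difference has an SE of √(1/12 + 1/6) = 0.5 SD, so it exceeds 0.5 SD in either direction in about 32% of randomisations. Given a baseline difference Δ, the expected last-value estimate shifts by rΔ, the change estimate by −(1 − r)Δ, and the covariate estimate by nothing. At r 0.82 with σ 33.3, a Δ of 0.5 SD is 16.7 points. The shifts are 0.82 × 16.7 = 13.7 and −0.18 × 16.7 = −3.0, on a true difference of 30. Averaged over all randomisations none of the three is biased.

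**Choice after seeing data.** In 40,000 simulated null trials at each r from 0.5 to 0.9, each analysis alone rejected about 5% of the time. Taking the smallest of the three p values rejected 9.6% to 10.8% of the time.

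**The case against.** The strongest reply is that change from baseline is plainly meant. The endpoint is a reduction, the power paragraph expects reductions of about 30%, and the models are to track change. On that view the last-observed sentence only says which visit counts. The low powers then come from a mismatch: sizing the trial on the SD of change and analysing levels. In either consistent pairing the plan has its stated 0.804. Against a change score the covariate gains little below r of about 0.85 and loses 1 to 3 points above it or with truncation. The trial is also a small proof-of-concept study that says its power cannot be derived definitively.

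Most of this stands, and it limits the size of the point. A reader might infer that the trial is underpowered, or that the sponsor means to ignore baseline. The documents support neither: the power figure reproduces, and the wording leans towards change. A reader might also infer that a covariate is clearly more powerful than change; at the correlations the documents suggest, it is not.

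What the reply does not supply is a model. No sentence says that the pre-treatment value is subtracted, adjusted for or modelled as an outcome, and the last-observed sentence still permits an unadjusted comparison.

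**Conclusion.** This is a gap in specification and not an error of calculation. It is worth closing because it concerns the primary endpoint and the data needed are already scheduled. Against an unadjusted last-value analysis, the covariate raises power from 0.56, 0.39 and 0.24 to 0.83, 0.81 and 0.79 (change SD 20; r 0.72, 0.82, 0.90), or from 0.80 to 0.97 or 0.997 (level SD 20; r 0.72, 0.82). Against a change score the power is about the same. The benefit there is an estimate unaffected by chance baseline imbalance, and a choice fixed in advance that keeps the type I error at 0.05 and not near 0.10.

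These figures rest on the assumed r, a two-sided test, an additive effect and complete data in 12 and 6 subjects. The synopsis plans to randomise 25 because of early withdrawals, which the figures do not model.

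**What to change.** In section 2.8.1, replace the last-observed-outcome sentence, for the primary endpoint, with one primary model: a mixed model with the 1, 3, 5 and 7 month anti-GRP78 Peptide 25 values as outcomes, the pre-treatment value as a covariate, and one named primary contrast, for example the arm difference at month 7. Leaving the last-observed sentence in place would keep the ambiguity. The outcome scale (OD, log OD or percent) is a separate choice that the covariate does not settle, and it should be stated in the same place.

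Use the same model in section 2.8.2 for the pneumococcal antibody and B-cell endpoints, where the last-observed rule is repeated.

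The cost is a sentence in each section and about one degree of freedom with a common baseline slope. Against a change score, 1 to 3 power points may be lost if r is very high or with truncation at entry. Against unadjusted values, about 3 points would be lost if r were 0 (0.804 to 0.773). No new samples or visits are needed.

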2.3 STUDY TREATMENTS

Following procurement of informed consent and completion of baseline screening assessments, patients that meet all inclusion/exclusion criteria will be randomly assigned to receive one of the two following treatments, starting on Day 1, in a ratio of 2:1.

1.) EXPERIMENTAL BELIMUMAB TREATMENT (n=12). Subjects randomized to the experimental treatment arm will receive i.v. administrations of belimumab (10 mg/kg), consisting of three "loading" doses, two weeks apart, followed by five (5) more monthly infusions. The final assessment will be performed at month 7 (see Table 1).

2.) PLACEBO CONTROLS (n=6): These subjects will be treated with identically appearing placebo i.v. on the same schedule as the experimental arm subjects (i.e., three "loading" doses, two weeks apart, followed by five more monthly infusions. The final assessment will be performed at month 7 (see Table 1).

		Loadi	ng Doses]			
Days	1	14	30	60	90	120	150	180	210
Study	х	Х	х	Х	х	Х	Х	Х	Assessment
Drug									only (final)

Table 1. Schedule of study drug infusions (either belimumab or placebo) and final assessment

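### Section 2.8.1 leaves open whether the last observed value or the mixed model decides the primary test, and the last-observed rule can put earlier values in place of the day-210 difference

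*Combined protocol and SAP*

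**What the plan says.** Section 2.8.1 gives two treatments of the same endpoint. First, "Repeated measures linear mixed models will be used to evaluate differences of immunological parameters", covering the primary and most secondary endpoints; these models are said to "allow for missing observations, which should be minimal". Then, as a general rule under intention to treat, the analysis proceeds "with the last observed outcome over all time points being used as the primary measure for a given variable".

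The power statement in the same section expects the antibody reduction "by or after approximately 6 months of therapy" and starts from "If the true difference in the experimental and control means is 30" per cent, with a standard deviation of 20 per cent. The assay description in 2.7.1 ends with "Optical densities (OD) are determined at 405 nm". Experimental blood is drawn "pretreatment, and on days 30, 90, 150, and 210 after the start of therapy" (2.6.4), and 2.3 adds: "The final assessment will be performed at month 7".

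Section 2.8.2 repeats the last-observed rule for the secondary endpoints, acknowledges that carrying observations forward has evident problems, and plans multiple imputation to examine them. Section 2.8.1 has no matching sentence. The synopsis (Planned Sample Size) randomises 25 subjects to end with 18, because of withdrawals under COVID-19 guidance and for medical reasons not related to study drug or procedures. Section 2.9.1 relies on the data analysis methods to keep the comparison meaningful if subjects drop out.

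**The concern.** A repeated-measures model uses every visit. A last observed value is one number per subject, taken at different times for different subjects. The two can give different answers, and 2.8.1 does not rank them. It also does not say whether the endpoint is analysed as optical density, log optical density or percent change.

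The last-observed rule has a second weakness in this trial. Samples fall at months 1, 3, 5 and 7, and the powered difference is expected from about month 6. Only the day-210 sample is late enough. For anyone who leaves before it, the rule substitutes a value taken before the expected effect. If the effect is still growing, the estimate is pulled towards zero even when people leave for reasons unrelated to outcome. The result is meant to help size later trials, so a diluted estimate would carry forward. The expectation of minimal missing data also sits badly with randomising 25 to obtain 18.

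**Working it through.** **1. The plan's own figure.** Inputs from 2.8.1: difference 30, SD 20, 12 v 6 subjects, alpha 0.05 (two-sided assumed, since the null is equality of means).

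- Standard error = 20 × √(1/12 + 1/6) = 20 × 0.5 = 10
- Noncentrality = 30/10 = 3.0 on 16 degrees of freedom; power = 0.804
- At 1:1, 8 per arm gives 0.797, so 16 v 18 subjects agrees with the stated cost of two extra subjects

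The figure reproduces. It is a comparison of two means and is not tied to a visit.

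**2. Early withdrawal.** 25 − 18 = 7, and 7/25 = 28%. This is an upper figure inferred from the synopsis. The documents give no exit times.

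**3. Expected last-observed estimate.** Assumptions: 25 randomised as 17:8, leavers at random, true day-210 difference 30 points. Let n_v be the number of subjects last seen at visit v and δ_v the effect at that visit.

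Estimate = Σ n_v δ_v / 25, with 18 subjects at month 7.

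Effects assumed at months 1, 3, 5, 7: linear 5, 15, 25, 30; early 10, 30, 30, 30; late 0, 0, 0, 30.

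| Leavers last seen at months 1/3/5 | Linear | Early | Late |
|---|---|---|---|
| 3/4/0 | (15 + 60 + 0 + 540)/25 = 24.6 | (30 + 120 + 0 + 540)/25 = 27.6 | 540/25 = 21.6 |
| 2/2/3 | (10 + 30 + 75 + 540)/25 = 26.2 | (20 + 60 + 90 + 540)/25 = 28.4 | 21.6 |
| 0/2/5 | (0 + 30 + 125 + 540)/25 = 27.8 | (0 + 60 + 150 + 540)/25 = 30.0 | 21.6 |

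Linear onset loses 7% to 18% (27.8/30 = 0.93; 24.6/30 = 0.82), early onset 0% to 8%. The late pattern is an extreme case and loses 28%. With three leavers, one each at months 1, 3 and 5, linear onset gives (5 + 15 + 25 + 660)/25 = 28.2. With no leavers the estimate is 30.

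**4. Power in the same patterns.** Simulation, 6,000 runs per cell, SD 20, assumed visit correlation 0.7. The model is baseline-adjusted with treatment-by-visit and a random subject intercept, tested at day 210 on 22 degrees of freedom. For reference, 17:8 with nobody leaving gives 0.918.

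| Onset | Last-observed t-test (3/4/0, 2/2/3, 0/2/5) | Day-210 model contrast |
|---|---|---|
| Linear | 0.736, 0.811, 0.863 | 0.863, 0.863, 0.858 |
| Early | 0.852, 0.879, 0.916 | 0.853, 0.862, 0.874 |
| Late | 0.550, 0.560, 0.562 | 0.847, 0.863, 0.863 |

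The model's estimates are 29.8 to 30.2 points throughout. Last-observed power is lower in five patterns, about equal in two and higher in two. The model was fitted with the covariance that generated the data, which favours it.

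**5. The covariance matters.** In null data with leavers 2/2/3 and an SD of change that grows over visits (assumed 8, 13, 18, 20), the random-intercept model has type I error of about 0.15, against about 0.05 for the last-observed t-test. A random intercept forces equal variance at every visit. The documents give no variance pattern, so a model of that form should not be fixed in advance.

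**The case against.** **A primary measure is named.** The text calls the last observed value primary; for completers that is day 210, and the power text states a null of equal arm means. A natural reading is that the last value is tested and the mixed model describes the course over time. This stands. A reader might infer that the plan has no primary analysis at all; the documents do not support that. What stays unstated is the ranking of the two analyses, the model contrast and the scale.

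**The mixed model is already a check.** It is a second planned analysis of this endpoint, uses all visits and tolerates gaps. This also stands: it would be wrong to say the last-observed rule goes unexamined for the primary endpoint. But the plan does not give the model that role, and only 2.8.2 plans imputation.

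**The effect may come early.** The power text allows for an effect by 6 months as well as after. If it is nearly complete by month 3, the loss is 0% to 8% and the last-observed test can have slightly more power. This stands, and is why the dilution is only an illustration.

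**A model can do worse.** This stands for a random-intercept-only covariance, as step 5 shows, and it shapes the fix.

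**This is a proof-of-concept trial.** That limits the severity. But the plan sets an alpha and a power and wants data to size later trials, which calls for one defined estimate.

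**Conclusion.** The point holds as an inexpensive improvement that should be made. Section 2.8.1 should say which analysis decides the primary test and on what scale, and a day-210 model contrast fits the powered difference better than a last value taken at mixed times. The size depends on assumed exit timing, onset shape and correlation: a loss of 7% to 18% under linear onset with 7 of 25 leaving, less with early onset or fewer leavers, none with no leavers. The bias is nil or towards zero in these patterns; power can be lower, equal or higher.

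Three stronger readings are not supported:

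- **The sample size is wrong.** It reproduces on its own inputs.
- **Exits are related to outcome.** The synopsis attributes the withdrawals to COVID-19 guidance and unrelated medical reasons. Section 5.6.4 also removes subjects with certain exacerbations, and 2.7.1 reports that optical density tended to rise as disease worsened, so a link cannot be excluded. No document quantifies one. Neither the model nor imputation would test it, since both assume missing at random.
- **The test runs above 5%.** In null simulations (12:6, no dropout, equal visit correlations of 0.5 to 0.9), taking the best of month-7 difference, visit average or slope gives about 10%. That requires choosing after seeing results, and nothing in the plan says this would happen.

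**What to change.** In 2.8.1, replace the last-observed clause with text such as:

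> The primary analysis is the treatment difference at day 210 in anti-GRP78 Peptide 25, adjusted for baseline, from the repeated-measures mixed model with treatment, visit, treatment-by-visit and baseline value, using all available visits of all randomised subjects. The covariance is unstructured (or heterogeneous-variance), with a small-sample degrees-of-freedom correction such as Kenward-Roger and a pre-stated simpler fallback if the model does not converge. The last-observed-value comparison and multiple imputation are sensitivity analyses.

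State one scale before unblinding: percent change from baseline, or log optical density back-transformed to a percent difference. Either is compatible with the 30% in the power statement, which gives no formula of its own. Delete the closing expectation in 2.8.1 that missing observations will be few. Do not prescribe a random-intercept-only covariance. A matching change in 2.8.2 is optional, for consistency.

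**Cost.** Wording only: no new visits, samples or subjects, and both methods are already in the plan. There are two statistical costs. Power is slightly lower than for the last-observed test in some early-onset patterns (at most 0.874 v 0.916 in the table, a difference of about 0.04). There is also some imprecision from estimating the covariance in a small trial. The power figures in the working are for the random-intercept form and do not include that second cost.
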